Vanderbilt Epicenter Advisory and Steering Committee: An advisory and steering committee comprised of individuals with expertise regarding various aspects of infection prevention, pathogen transmission, occupational health, HCP protection, use of PPE, and environmental safety will be created to guide the Epicenter's research program. Facilitated by the Vanderbilt Epicenter program coordinator, this committee will meet quarterly to assess progress on the epicenter projects, advise the development of new study protocols, review responses to new call for proposals set forth to the epicenter network, and assess barriers to study completion. We will invite and encourage CDC Epicenter leader participation at these sessions to ensure tight communication with and guidance from these partners. The following individuals have agreed to serve as initial members of the Vanderbilt Epicenter Advisory and Steering Committee:

#### Specific Aims of the Vanderbilt Epicenter Research Plan:

The proposed Vanderbilt Epicenter research plan outlined below is designed to examine several important issues surrounding pathogen transmission, use and misuse of PPE, and methods to improve the protection of HCP and their patients. The proposed studies also harness Vanderbilt's expertise in the use of simulation training and tools (Aim I), monitoring and feedback of practice compliance using a model of shared accountability (Aim II), and the performance of quasi-experimental studies of infection prevention interventions in an operational setting (Aim III). Successful completion of the proposed studies will improve the capacity to prevent and control the spread of EVD, MDROs, *C. difficile* and other infectious pathogens with similar modes of transmission in healthcare settings, thereby helping to prevent and control both current and future outbreaks.

**Specific Aim I:** To examine risk factors for HCP self-contamination with the donning, use, and doffing of PPE used for Contact, Droplet, and EVD-Specific Precautions using simulation laboratory techniques.

**Specific Aim II:** To evaluate in a variety of clinical care settings the effectiveness of a standardized PPE compliance auditing tool coupled with a tiered accountability framework.

**Specific Aim III:** To investigate the impact of preemptive Contact Precautions for residents of long-term care facilities admitted to acute care units, including the impact on the rate of hospital acquisition of MDRO and C. difficile and unintended consequences (e.g. frequency of HCP contacts, patient falls) due to this isolation strategy.

Specific Aim I: To examine risk factors for HCP self-contamination with the donning, use, and doffing of PPE used for Contact, Droplet, and EVD-Specific Precautions using simulation laboratory techniques.

**SIGNIFICANCE:** This project will use simulation to evaluate and examine risk factors for HCP self-contamination with the donning, use, and doffing of PPE used for Contact, Droplet, and EVD-Specific Precautions. Several studies suggest that PPE training maybe inadequate and may vary by type of HCP and clinical area. In examining issues with PPE effectiveness, it is important to evaluate PPE use under a variety of clinical circumstances. Conducting such investigations using HCP engaged in actual patient care can be very challenging. As such, recent studies have investigated PPE use and the risk of self and environmental contamination using simulation assessments. Using a non-pathogenic bacteriophage (MS2) and simulation training, Casanova *et al* examined the risk of contamination and breaches with the use PPE among 10 volunteers. Following the donning of PPE (gown, gloves, eye protection, and an N95 particulate respirator) that were contaminated with MS2 at strategic locations, the study subjects measured blood pressure on a simulation manikin and then doffed the PPE components. Bacteriophage contamination of the hands and underlying clothing of the volunteers occurred in a majority of instances (hand contamination 70-90%, clothing 75-100% of instances).

Investigators at the University of Nebraska Medical Center also employed simulation assessment to examine donning, use, and doffing of the PPE used with Contact (i.e. gown and gloves) and Airborne (i.e. N95 respirator) Precautions. Ten HCP volunteers were observed using video monitoring for breaches in recommended practices while performing a simulated patient care scenario. These breaches were assessed independently by three study investigators. Fluorescent markers (Glo Germ™ powder) were also placed on strategic locations in the simulation room, including on the patient's gown front and arms, the bedside table, and the bed handrails. Following PPE doffing, each subject was examined for selfcontamination of the fluorescent powder. Every participant committed at least one breach in PPE use, including touching unprotected areas of the body with contaminated PPE and unnecessary touching of surfaces in the room. Contamination with the fluorescent powder was detected on 80% of the subjects.

In a follow up investigation, this team examined compliance with isolation practices among 24 nurses using a simulated patient care setting. Using methods similar to those noted above, poor compliance with PPE donning, in-room PPE use, and PPE doffing was noted. Example breaches included failure to tie gowns at the neck, touching of the face or other nonprotected areas with contaminated gloves, and failure to doff PPE as per recommendations.

Casanova *et al* compared the use of single vs. double gloving while performing a vital signs assessment on a simulation manikin and the risk of MS2 nonpathogenic bacteriophage contamination of the PPE components and participant hands. Among the 18 HCP volunteers, hand contamination with MS2 was significantly more frequent with the use of a single pair of gloves (occurring in 78% of volunteers vs. only 28% of volunteers when double gloving was utilized, *p* = 0.006). Errors in PPE removal were frequent in both scenarios (72% with any error in double gloving scenarios; 67% in the single gloving scenario). Importantly, contamination occurred even with a visible PPE removal protocol present for reference during the scenario, suggesting the need for additional strategies to improve compliance along with these "just-in-time" reminders.

Lai *et al* examined the risk of contamination with different glove removal techniques using a fluorescent solution. Glove removal using any technique led to environmental contamination. Wong and colleagues identified a variable risk of HCP contamination between different types of PPE (gowns or aprons) using simulated respiratory secretion exposure with a fluorescein solution. A randomized crossover study of 50 subjects wearing novel respiratory pathogen precautions PPE (gloves, gown, N95 particulate respirator, face shield, and hair cover with and without a powered air-purifying respirator [PAPR]) also used fluorescein solution to assess contamination with PPE use. The solution was atomized onto the HCP while in the PPE,

[figure not shown]
mimicking exposure to respiratory droplets. Contamination was greater in those who did not wear the PAPR, with the anterior neck, forearms, wrists and hands the most common areas of contamination.

Finally, Guo *et al* examined the risk of breaches and environmental contamination with the use of three types of protective gowns and two different recommended strategies of gown removal. Contamination was assessed using a fluorescent lotion (detected by ultraviolet units) mixed with olive oil and water to mimic infectious aerosol particles. Subjects received video training on the use of PPE and, once PPE was donned, were exposed to a spray of lotion on the upper torso. PPE was then doffed in a separate area. Environmental contamination was significantly lower when using a gown removal method that pulled the gown away from the wearer during doffing. The researchers also noted that hand contamination was significantly higher among subjects who had at least 16 years of clinical experience (perhaps due to a false sense of competency with PPE use), while nurses had a higher rate of shoe contamination when compared to other provider types. A cotton gown was associated with lower contamination of the environment when compared to a water-resistant gown and a disposable plastic apron; however, undergarment contamination was increased with use of the cotton gown.

While these studies are advancements in the understanding of and risk for breaches in PPE use, there are several key limitations. First, the number of HCP studied was relatively limited, in part due to the complexities and costs of simulation assessments (Figure 2). Second, the simulation scenarios involved single patient care tasks (e.g. blood pressure assessment) rather than a more complex patient interaction than is common during patient care. Finally, the duration of the scenarios were short and may not have captured issues and risk factors associated with more prolonged PPE use.

For this study Aim, we will utilize the expertise of investigators from the Vanderbilt Center for

Experiential Learning and Assessment (CELA). Directed by [name] (an Epicenter Investigator), CELA is an advanced facility with of several interrelated programs, including human simulation using standardized patients and technical simulation utilizing state-of-the-art manikins. CELA optimizes the benefits of simulation by means of deliberate practice and multiple layers of thoughtful feedback and assessment, with a view towards enhancing professional

communication skills and the mitigation of human error in the delivery of patient care. We aim to assess the frequency of and risk factors for PPE breaches using a larger study population and more complex scenarios that mimic typical patient care activities during which PPE is used.

**INNOVATION:** The main innovation of this study Aim is that the majority of prior studies were on single evaluations of PPE breaches (double vs single gloves as example), where the current study will be comprehensive and employ longer and more complex scenarios that mirror actual HCP activities. In addition, 3 different precaution scenarios will be assessed. We will also use a cohort of HCP that is larger than in published investigations of this issue. We believe that patient care settings will not provide this opportunity because such activities usually occur in time-pressed, uncontrolled environments where patients must take precedence. Simulation has been

widely touted as a tool to improve clinical care and patient safety. It is a broad construct that ranges from role-playing to full-scale manikin-based Realistic Patient Simulation (RPS) and includes standardized patients (SP) and partial task trainers of varying sophistication. Realistic Patient Simulations can involve fully interactive simulation environments containing all clinical equipment and cues found in the patient care environment. The manikin to be used in this project (SimMan™) is a computer-controlled plastic patient that generates or emulates physiological findings (e.g. ECG, invasive and non-invasive blood pressure, lung sounds, palpable pulses). The manikin's head contains a speaker so that the participant can converse with the 'patient' when contextually appropriate. The manikin responds to clinical interventions just as a patient would. Thus, participants interact with a realistic cognitive and physical representation of the full acute care environment and thereby experiences emotional and physiologic responses similar to those experienced in real situations.

We will also use Standardized Patients (SP). SPs are persons recruited and trained to simulate an individual with a specific clinical story and respond accurately and reliably to questions regarding the medical condition or illness portrayed during a clinical encounter. SPs are trained to communicate emotional or contextual aspects of the scenario. The concept of SP has been applied to a wide range of training and assessment exercises that now include standardized family members, clients, standardized examinees and members of healthcare teams. In this study, we will use SPs as well as Simulated Clinicians (SC) who as team members will enhance the realism of the scenario. SPs have been effectively used in healthcare research, including clinician training, quality improvement and patient safety. Successful completion of this Aim will result in an in depth-understanding of the frequency of and risks for lapses in PPE use and will inform the development of a standardized PPE compliance audit tool for use in a wide array of healthcare settings. Implementation of this tool will be the focus of Aim II. This may also lead to further studies on the use of these tools and infrastructure to train HCP on appropriate PPE use.

#### APPROACH:

#### **RESEARCH DESIGN AND METHODS:**

**Study design:** High-fidelity simulation experiments performed using three transmissionbased precaution scenarios.

**Study eligibility:** HCP will be recruited for participation in the experimental assessments. The target sample size is 150 subjects with an explicit goal for a diversity of HCP types (i.e. physicians, nurses, and house staff). Eligible subjects must be currently working in a healthcare setting. Because the intricacies of EVD-specific precautions, for the scenarios focused on this type of precautions, volunteers will be recruited from members of the Vanderbilt Communicable Disease Response Team (CDRT). The CDRT consists of HCP from the following disciplines: nurses, physicians (including Epicenter Investigators [name] and [name]), paramedics, and educators. Each team member possesses knowledge and/or skills necessary to care for patients who require intensive medical care. Each volunteer also receives intensive periodic (quarterly) training in the care of patients with highly communicable, serious infectious diseases. Training includes specific disease pathology, PPE use, and EVD infection prevention protocols. Participants will be paid for participation in this study.

#### **Study locations:**

[figure not shown]
**Center for Experiential Learning and Assessment (CELA):** Most of the experiments will occur in the Vanderbilt CELA. This is an 11,000+ sq. ft. facility that includes a 1,100 sq. ft. simulation suite for manikin-based simulation. This structure allows two separate simulations to run simultaneously, configured jointly as a six-bed ED, four-bed ICU or PACU, or a combination of these, or to be a large single simulation suite that can be used for simulations. The suite also has a virtual reality training room, available 24/7, equipped with the latest in virtual reality simulators and partial task trainers designed to train advanced medical procedures.

Another core program involves the use of SP in simulations. This program is housed in a 7000 sq. ft. suite which consists of 12 fully equipped exam rooms, with the latest audiovisual and computer capabilities and one-way viewing mirrors into the exam rooms. Additional facilities are a designated student orientation room equipped with full audiovisual capabilities, a private observation room with monitors to watch student encounters and provide feedback through a software interface, two control rooms for operating the center's audio visual and software components, and a standardized patient lounge for use during events as well as a dedicated conference room for SP training and overflow during full capacity.

**Communicable Disease Response Unit (CDRU):** For the EVD-Precautions scenarios, we will also utilize the Vanderbilt CDRU. The CDRU (Figure 3) is a state-of-the-art facility designed for the care of a patient with a rare or unknown, highly communicable disease, such as EVD or MERS-CoV. The unit consists of several distinct areas: patient room, anteroom, PPE doffing area, and nurse's station. It provides a safe environment to care for patients while protecting staff, other patients, and the local community. Patient is care is provided by the CDRT.

## Study procedures:

Three transmissionbased precaution scenarios will be utilized (Table 2). These will involve Contact Precautions (PPE: gown and gloves), Droplet Precautions (PPE: surgical mask), and EVD-Precautions (PPE: PAPR, eve protection, hood, aown. double aloves. lea

coverings, and apron). For the Contact Precautions scenario, subjects will perform a brief history and abbreviated physical exam along with a simulated wound dressing change. For the Droplet Precautions scenario, subjects will perform a brief history and abbreviated physical examination along with management of a urinary catheter (including emptying of collection bag). For the EVD-Precautions scenario, subjects will perform a brief history and abbreviated physical exam along with medication administration through an intravenous catheter. Non-CDRT personnel will participate in both the Contact and Droplet scenarios (A-D in Table 2), while only CDRT members will participate in the EVD-Precautions scenario (E & F in Table 2). Each

scenario will have a standard 10 minute duration and a prolonged 20 minute duration (in which the exam is a standard physical exam) to assess the impact of prolonged PPE use on compliance.

Using a fluorescent compound to reproduce contaminants in assessing

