Factors that affect the appropriate use of PPE are numerous, complex, and not fully **understood.** A deeper understanding of the factors that impact the use of PPE has emerged over the past 15 years, prompted to a degree by the SARS experience. Shigayeva and colleagues performed a retrospective cohort study of 795 HCP who cared for critically-ill SARS patients in the window surrounding patient intubation. The HCP reported substantial breaches in the use of recommended barrier precautions (i.e. gloves, gown, masks, and eye protection), and the frequency of noncompliance declined over time, suggesting improvement as familiarity and comfort with the PPE increased. The following factors were significantly associated with an increased self-reported consistent compliance to PPE: recognition of patient as a SARS case (odds ratio [OR] 2.5, 95% confidence interval [CI] 1.5-4.5), recent infection control training (OR 2.7 for interactive training, 95% CI 1.7-4.4) and work in a SARS (OR 4.0, 95% CI 1.8-8.9) or intensive care (OR 4.3, 95% CI 2.0-9.0) unit. Conversely, provision of care of patients with higher Acute Physiology and Chronic Health Evaluation (APACHE) II scores (OR 0.4 for score ≥20, 95% CI 0.28-0.68) and work on shifts that required more than 6 room entries per shift (OR 0.5, 95% CI 0.32-0.86) were significantly associated with lower reported frequency of consistent compliance.

An in-depth assessment of 15 HCP who acquired SARS after implementation of isolation precautions during the 2003 outbreak identified several key issues. Only 60% reported having received formal infection control training, 87% were unsure of proper PPE use, and 40% reused PPE and other items following their use for the care of a SARS patient. Strikingly, 54% reported an identified breach in the use of SARS infection control precautions during patient care. While the SARS-CoV is spread in a somewhat different fashion than pathogens like Ebola or MDROs (airborne vs. direct contact), the insights gained regarding the risk of PPE breaches greatly inform such risk for all types of PPE.

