#### Study outcomes and assessment:

1) Lapses in PPE use: These will be captured via video monitoring and recording of each subject experiment from PPE donning through PPE doffing. Two independent investigators will review every scenario and note the frequency and type of breaches in the use of PPE. Investigators will be trained on a standardized method for reviewing each scenario and will use a standardized abstraction tool. The time of the lapse in relation to scenario start will be captured to examine the impact of the duration of PPE use.

2) HCP and environmental contamination: Contamination will be assessed using ultraviolet light inspection of the subjects following doffing of PPE and of the simulation room environment to assess for the number of contamination events during each scenario. The rooms will be cleaned prior to each experiment to avoid cross-contamination.

**Analysis:** A descriptive analysis of the frequency (number per minute of scenario time), number, and types of lapses in PPE use will be performed. The number of self and environmental contamination events (defined as an identified patch of fluorescent powder located in these areas) will also be described as a quantitative number and an event rate per minute of scenario time. Lapse and contamination rates will be compared between each scenario type (Contact, Droplet, and EVD), scenario duration (standard vs. prolonged), and HCP type (physician, nurse, other) using Student's t-test or Wilcoxon Rank Sum test (for duration comparison) and ANOVA or Kruskal-Wallis analysis (for precaution type and HCP type comparison given >2 study groups). For categorical outcomes (e.g. the number of lapses) Fisher's Exact Test will used for comparisons.

**Limitations:** Even with a larger study cohort, the sample size will limit the ability to examine nuanced details in patient care while wearing PPE that lead to lapses. Nonetheless, this will be one of the largest and most complex simulation experiments on PPE use published to date.

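### Aim I: EVD precautions and response-team training are fully aliased, so the three-group precaution-type test and both EVD contrasts cannot separate them; Contact versus Droplet is not affected by team membership

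*Protocol*

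**What the plan says.** Aim I, Study procedures, divides the scenarios by team. For the first two precaution types it says: "Non-CDRT personnel will participate in both the Contact and Droplet scenarios (A-D in Table 2"). The third type is reserved for the response team; the text there is that "only CDRT members will participate in the EVD-Precautions scenario (E & F in Table 2").

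Aim I, Study eligibility, gives the complexity of EVD precautions as the reason for this restriction and describes the team's preparation: "Each volunteer also receives intensive periodic (quarterly) training in the care of patients with highly communicable, serious infectious diseases". On the content of that preparation, the same paragraph says: "Training includes specific disease pathology, PPE use, and EVD infection prevention protocols".

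The Aim I Analysis paragraph then puts all three types into one comparison: "Lapse and contamination rates will be compared between each scenario type (Contact, Droplet, and EVD), scenario duration (standard vs. prolonged), and HCP type". The test named is "ANOVA or Kruskal-Wallis analysis (for precaution type and HCP type comparison given >2 study groups"). No covariate is named. The Limitations paragraph of Aim I mentions sample size only.

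The Significance section, in its discussion of factors that affect PPE use, reports training as a correlate of self-reported consistent compliance in a retrospective cohort of staff who cared for SARS patients: "recent infection control training (OR 2.7 for interactive training, 95% CI 1.7-4.4").

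**The concern.** Aim I is meant to identify risk factors for self-contamination. PPE type is one candidate factor and training is another. As planned, everyone in EVD equipment belongs to the drilled team, and everyone in Contact or Droplet equipment comes from outside it. Any EVD difference, or lack of one, may reflect the equipment, the training or both.

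The protocol's own background treats training as important for compliance, so this is not a remote possibility. The protocol also expects the Epicenter results to inform guidelines and policies (Translation of Epicenter Findings). A formal p-value for precaution type that includes EVD could be read there as a finding about the equipment. The missing overlap is fixed by the design, so a later analysis plan cannot supply it.

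**Working it through.** The protocol gives no power, effect size or alpha for Aim I, so there is no stated figure to reproduce. The check has three steps.

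**1. Can the EVD effect be estimated?** Code the six cells of Table 2 with an intercept, Droplet, EVD and CDRT:

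| Cells | Intercept | Droplet | EVD | CDRT |
|---|---|---|---|---|
| A, B (Contact) | 1 | 0 | 0 | 0 |
| C, D (Droplet) | 1 | 1 | 0 | 0 |
| E, F (EVD) | 1 | 0 | 1 | 1 |

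The EVD and CDRT columns are identical (correlation 1.0), and the matrix has rank 3 for 4 columns. Only the sum of the EVD and CDRT effects can be estimated. The Droplet-minus-Contact contrast does not involve the CDRT column. Nor do A versus B, C versus D or E versus F, so duration within a type is also clear of it. If CDRT members also did A-D, the rank would be 4 of 4 and the two effects could be separated under an additive model.

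**2. How far could training shift the EVD contrast?** This is an illustration. From the protocol: odds ratio 2.7, interval 1.7 to 4.4. Assumed: untrained compliance p of 60% or 75%, a true two-fold excess of non-compliance with EVD PPE, and transfer of the odds ratio to this setting.

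- Odds with training = OR × p/(1 − p)
- Compliance with training = odds/(1 + odds)
- Non-compliance ratio = (1 − compliance with training)/(1 − p)
- Apparent EVD ratio = 2 × non-compliance ratio

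| OR | p | Odds with training | Compliance with training | Non-compliance ratio | Apparent EVD ratio |
|---|---|---|---|---|---|
| 1.7 | 0.60 | 1.7 × 1.5 = 2.55 | 0.718 | 0.282/0.40 = 0.70 | 1.41 |
| 1.7 | 0.75 | 1.7 × 3 = 5.1 | 0.836 | 0.164/0.25 = 0.66 | 1.31 |
| 2.7 | 0.60 | 2.7 × 1.5 = 4.05 | 0.802 | 0.198/0.40 = 0.50 | 0.99 |
| 2.7 | 0.75 | 2.7 × 3 = 8.1 | 0.890 | 0.110/0.25 = 0.44 | 0.88 |
| 4.4 | 0.60 | 4.4 × 1.5 = 6.6 | 0.868 | 0.132/0.40 = 0.33 | 0.66 |
| 4.4 | 0.75 | 4.4 × 3 = 13.2 | 0.930 | 0.070/0.25 = 0.28 | 0.56 |

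Across the interval, the same true excess could appear as a moderate excess (1.41), as no difference, or as a reversal (0.56).

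**3. What would the planned test do if only training mattered?** This was simulated with 4,000 runs per setting. All settings are assumptions: 150 independent subjects, normal outcomes with SD 1, non-CDRT staff split equally between Contact and Droplet, no true precaution effect, and a training-only shift in the EVD group. The share of ANOVAs with p < 0.05 was:

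| CDRT subjects | No shift | 0.3 SD | 0.5 SD | 0.8 SD |
|---|---|---|---|---|
| 20 | 5% | 19% | 43% | 86% |
| 30 | 6% | 24% | 57% | 94% |
| 50 | 5% | 33% | 73% | 99% |

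Kruskal-Wallis gave similar results (40%, 54% and 71% at 0.5 SD). A significant precaution-type result is therefore no evidence by itself that the equipment matters.

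**The case against.** The best defence is that the Analysis paragraph only says that rates will be compared. It states no hypothesis about EVD, makes no causal claim, and begins with description. Staffing can be seen as part of EVD precautions as delivered: the protocol explains why only the team does these scenarios and says that the team provides care in the Communicable Disease Response Unit. EVD as delivered against Contact as delivered can be estimated.

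Part of this stands. The restriction to the team has a stated reason and is not in dispute, and a comparison of delivered packages is legitimate if it is labelled as one. But the protocol does not label it so. It enters EVD as a level of precaution type in an inferential test, within an Aim about risk factors, and its limitations do not mention the overlap.

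Other points limit what can be claimed:

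- A reader might take the central odds ratio and conclude that a two-fold EVD excess would appear as 0.9-1.0, that is, vanish. The documents do not support that. The cited interval widens the range to 0.56-1.41, the baselines and the two-fold excess are assumed, and the odds ratio concerns self-reported compliance, not observed lapses or fluorescent patches.
- A reader might infer that the contrast would misdirect the Aim II audit tool. Aim II, Tool Development, bases the tool on the kinds of breach seen and the practices behind them, not on a between-type test. No link to the EVD contrast is stated.
- A reader might infer that EVD equipment would falsely reassure unprepared hospitals. The Significance section itself says that safe EVD care needs intensive preparation that only some facilities can provide.
- The protocol does not expressly bar CDRT members from scenarios A-D. Separate groups are the natural reading, and no CDRT data in A-D are planned.

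**Conclusion.** The point holds for the three-group test and for EVD versus Contact and EVD versus Droplet. In these, precaution type and team training are completely aliased, and no covariate, model or matching can separate them. This conclusion needs only the protocol's assignment of staff to scenarios, not the odds ratio or the simulation.

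The size and direction of the distortion are unknown. The range of about 0.56 to 1.41 for an assumed two-fold excess shows how little the contrast could tell; it is not an estimate of bias.

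It would go too far to call the whole precaution-type analysis void. Contact versus Droplet and the within-type duration comparisons are not affected by team membership. Contact versus Droplet does carry a separate, smaller caveat: each type has its own clinical task (wound dressing, urinary catheter, intravenous medication) and one powder site of its own. EVD is also tied in part to location, because its scenarios also use the Communicable Disease Response Unit.

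**What to change.** Amend the Aim I Analysis and Limitations paragraphs:

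1. Limit the inferential precaution-type test to Contact versus Droplet in non-CDRT volunteers. Make it a within-person comparison, because the same staff do both and their results are not independent.
2. Report EVD lapse and contamination rates descriptively with confidence intervals, labelled as applying to CDRT-trained staff.
3. State as limitations that EVD is confounded with training and partly with location, and that precaution type is also tied to clinical task and powder site.

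This changes wording only. The price is the loss of a formal p-value for EVD, which could not have been interpreted as an effect of precaution type.

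Optionally, CDRT volunteers could also run a Contact scenario, so that EVD and Contact are compared within the same people. The cost is more than the scenario time: each extra run needs donning, doffing, ultraviolet inspection, room cleaning and video review by two investigators. It would remove the team confounding only; task, powder site and possibly room would still differ.
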